1.0 STUDY OBJECTIVES

1.1 Specific Aims

- 1.1.1 Specific Aim 1a: Conduct a RCT to evaluate reductions of methamphetamine use and HIV sexual risk behaviors, and increased advancement along the HIV Prevention or Care Continuum using a two-arm RCT to determine intervention effects through comparison of the Immediate Delivery [ID] (n=150) and Delayed Delivery [DD] (n=150) arms.
- 1.1.2 Specific Aim 1b: Evaluate reductions in methamphetamine use and HIV sexual risk behaviors, and increased advancement along the HIV Prevention or Care Continuum using an observed treatment effects analysis powered for prospective sub-group analyses to compare longitudinal pre/post data from the pooled ID and DD arms (n=300);
- 1.1.3 Specific Aim 1c: Evaluate reductions in methamphetamine use and HIV sexual risk behaviors, and increased advancement along the HIV Prevention or Care Continuum using a two-arm historical matched comparison design to evaluate the outcomes of the *Getting Off* app (ID+DD; n=300) relative to a matched sample of participants having previously attended the brick-and-mortar group-based *Getting Off* intervention (n~600; total n=900).

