2.2.6 Preliminary Studies: Lessons Learned

Three components addressed feasibility: 1) Physical location versus computer delivery: Could the *Getting Off* intervention, written to be delivered in a treatment clinic, be successfully delivered through an app?, 2) Clinical versus self-directed: Could the *Getting Off* intervention, originally designed to be delivered by a counselor, be self-directed? and, 3) Group versus individualized: Could the *Getting Off* intervention, originally designed for a group format, be individualized? Findings demonstrated proof-of-concept for the *Getting Off* app. *Getting Off* was easily delivered as a mHealth intervention; participants were engaged, were able to understand the CBT concepts, and thoroughly navigated through the sessions. Overall, satisfaction was very high. Areas for improvement that were identified: increased interactivity between the user and the avatar; an accumulation of points that could be used to “purchase” items to personalize and enhance the avatar (e.g., a computer, clothes, a dog); reduce text in certain sessions; and, increased gamification.

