8.3 HIV Sexual Risk Behavior

HIV sexual risk behavior outcomes will be assessed at all time points throughout the study, and will be operationalized dichotomously (e.g., incident STI via biomarker testing), as a counted variable (e.g., number of days/times engaged in CAI in the past 30 days), and as a continuous variable (e.g., a HIV risk severity index generated from multiple factor-analyzed items). Power calculations for engagement in HIV sexual risk behaviors assume a 65% probability of engagement during the pre-intervention period for participants in the DD arm (equivalent to ~2:1 odds of engagement). Multivariable inferential analyses of dichotomous outcomes will take the form of GLMs employing the Bernoulli family and logit link function; counted outcomes will be analyzed with GLMs employing the Poisson-log or negative binomial link functions as distributional patterns dictate (note: if data evidence an over-representation of zeros or an overdispersion of variance, zero-inflated Poisson and/or negative binomial analyses may be substituted); continuous outcomes will be analyzed using GLMs employing the identity link and Gaussian family functions and assume a single covariate unless otherwise stated (note: iteratively reweighted, bootstrapped, or jack-knifed estimation procedures may be used in Gaussian models if sensitivity analyses indicate undue influence from outliers). Mixed effects GLM models are considered the best linear unbiased estimators for repeated measures data employing non-parametric and/or limited dependent variables. All power calculations are premised on tests of association across two time points (e.g., baseline with app completion; app completion with brick-and-mortar program completion), providing the most conservative estimate of minimum detectable effect (MDE) size estimations; all power calculations assume $\alpha \leq 0.05$ (two-tailed), and $1 - \beta = 0.80$.

Table 2: Instruments, Targets, Variable Operationalizations, and Minimum Detectable Effects

Table 2: Instruments, Targets, Variable Operationalizations, and Minimum Detectable Effects (1 - β = 0.80; α = 0.05, two-tailed)

Instrument	Target	Variable Operationalizations			Power-- Minimum Detectable Effects		
		Dichotomous (Di)	Count (Cu)	Continuous (Co)	Model 1— RCT (Aim 1a; n=150/n=150)	Model 2— Tx Effects (Aim 1b; N = 300)	Model 3— Matched Comparison (Aim 1c; N = 300/N ~ 600)

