9.2 Specific Aim 1c Analysis

Aim 1c provides a non-inferiority trial against the group-based, brick-and-mortar intervention upon which the app is based, and will be a historical matched comparison analysis whereby pooled data from the proposed study (i.e., ID+DD, N=300) is contrasted against historical data from participants who have attended the brick-and-mortar Getting Off intervention after 2012 (N~600; matched according to age, race/ethnicity, and HIV status [see Random Assignment]). The proposed analytical model allows for non-inferiority analyses comparing the relative efficacies of brick-and-mortar vs. mHealth delivered intervention content. Power Calculations for Specific Aim 1c: estimated historical matched comparison MDEs for HIV Prevention or Care Continuum outcomes related to Specific Aim 3c are: 1) Di—OR = 1.52; 2) Cu—IRR = 1.30; 3) Co—f2 = 0.01; for methamphetamine use outcomes: 1) Di—OR = 0.62; 2) Cu—IRR = 0.90; 3) Co—f2 = 0.01; for HIV sexual risk outcomes: 1) Di—OR = 0.66; 2) Cu—IRR = 0.87; 3) Co—f2 = 0.01.

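### Aim 1c states no allowance for correlation among men treated in the same group, so its 80% power holds only if their outcomes are independent

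*Combined protocol and SAP*

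**What the plan says.** Section 1.1.3 describes the comparator as a "matched sample of participants having previously attended the brick-and-mortar group-based" version of the intervention. The Aim 1c analysis section (the second of two numbered 9.2) states: "Aim 1c provides a non-inferiority trial against the group-based, brick-and-mortar intervention upon which the app is based". There, "pooled data from the proposed study (i.e., ID+DD, N=300) is contrasted against historical data", and the historical sample is described as "historical data from participants who have attended the brick-and-mortar Getting Off intervention after 2012 (N~600; matched according to age, race/ethnicity, and HIV status". Section 2.2.4 gives the tailored programme as 24 sessions over 8 weeks. Section 2.2.6 treats the change of format as a feasibility question in its own right: could an intervention "originally designed for a group format, be individualized"?

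On analysis, section 8.1 plans mixed effects GLMs for Aims 1a to 1c without listing the random effects. Section 8.3 gives the reason for that choice: "Mixed effects GLM models are considered the best linear unbiased estimators for repeated measures data". Table 2 is headed "Minimum Detectable Effects (1 - β = 0.80; α = 0.05, two-tailed". For Aim 1c it lists dichotomous effects of OR 1.52 (HIV continuum), 0.62 (methamphetamine use) and 0.66 (sexual risk). Section 8.3 bases all power calculations on two time points, "providing the most conservative estimate of minimum detectable effect (MDE) size estimations".

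The documents give no ICC, design effect, group size, group identifier or group-level term. They do not say whether groups were closed or took new members on a rolling basis, and they state no non-inferiority margin.

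**The concern.** Men who attend the same sessions in the same weeks share peers, a facilitator and a calendar period, so their outcomes may be correlated. If so, 600 group attendees carry less information than 600 independent men. Two separate consequences follow:

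- An analysis that leaves the correlation out reports too small a standard error for the app-versus-group contrast.
- An analysis that includes it has less power than the plan states.

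Aim 1c carries the non-inferiority conclusion. Whatever margin is eventually set, an interval that is too narrow makes it easier to declare the app no worse.

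**Working it through.** **Inputs from the documents.** 300 app users and about 600 historical attendees (Aim 1c analysis section); two-sided alpha 0.05 and power 0.80 (Table 2); base rates p of 0.30, 0.80 and 0.65 (sections 8.2 and 8.3); stated ORs of 1.52, 0.62 and 0.66.

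**Assumptions.** ICC 0.05, range 0.01 to 0.10. Men per group m from 5 to 20. For a middle value, suppose one closed group at a time, back to back, from the start of 2013 to about August 2021 (RCT start as read from Table 1). That is 8.58 years × 52 / 8 = 55.8, or about 56 cycles, and 600 / 56 = 10.7 men per cycle.

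**Formulas.**
- App-side rate: pA = OR·p/(1−p) ÷ [1 + OR·p/(1−p)]
- Design effect, historical sample only: DE = 1 + (m−1)·ICC
- SE = √[pA(1−pA)/300 + DE·p(1−p)/600]
- Power = Φ(|pA−p|/SE − 1.96)

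**Step 1: reproduce the plan (DE = 1).** For the continuum outcome, the odds are 0.4286 × 1.52 = 0.6514, so pA = 0.3945 and the difference is 0.0945. SE = √(0.000796 + 0.000350) = 0.0339, and power = Φ(2.790 − 1.960) = 79.7%. The same steps give 80.9% for methamphetamine use and 81.6% for sexual risk. Solving for exactly 80% power gives ORs of 1.523 / 0.623 / 0.666 against the stated 1.52 / 0.62 / 0.66, all within 0.01.

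The convention matters a little. A pooled variance gives 80.6 / 82.8 / 82.1% power. Putting the base rate in the app sample instead gives detectable ORs of 1.51 / 0.634 / 0.669. All of these use DE = 1, which indicates that no clustering allowance was built in.

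**Step 2: apply the design effect.** Continuum outcome at ICC 0.05 and m = 10.7: DE = 1 + 9.7 × 0.05 = 1.485, so 600 men act as 600 / 1.485 = 404. SE = √(0.000796 + 1.485 × 0.000350) = 0.0363, and power = Φ(2.604 − 1.960) = 74.0%.

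**Step 3: error rate if clustering is ignored.** With equal outcome variances, the true SE exceeds the reported one by r = √[(1/300 + DE/600) ÷ (1/300 + 1/600)] = √[(2 + DE)/3]. The two-sided rate is 2[1 − Φ(1.96/r)]. At DE = 1.485, r = 1.078 and the rate is 6.9%. A 20,000-run beta-binomial simulation with 56 groups of 10 or 11 and a true rate of 0.80 in both samples also gave 6.9%.

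| ICC | m | DE | 600 act as | Power %, continuum / methamphetamine / sexual risk | Nominal 5% test runs at |
|---|---|---|---|---|---|
| 0.01 | 5 | 1.04 | 577 | 79.2 / 80.5 / 81.2 | 5.2% |
| 0.01 | 20 | 1.19 | 504 | 77.4 / 78.9 / 79.4 | 5.7% |
| 0.05 | 5 | 1.20 | 500 | 77.3 / 78.8 / 79.3 | 5.8% |
| 0.05 | 10.7 | 1.485 | 404 | 74.0 / 75.8 / 76.0 | 6.9% |
| 0.05 | 20 | 1.95 | 308 | 69.0 / 71.2 / 70.9 | 8.8% |
| 0.10 | 10.7 | 1.97 | 305 | 68.8 / 71.0 / 70.7 | 8.8% |

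Starting instead from exactly 80% with equal variances, ICC 0.01 gives 79.5% at m = 5 and 77.5% at m = 20. At ICC 0.05 and m = 10.7, the ORs detectable with 80% power become about 1.57 / 0.605 / 0.646.

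**The case against.** The strongest reply is that the size rests on numbers found nowhere in the documents. That stands. The figure of 10.7 men supposes a single closed group running back to back. Parallel groups would be smaller, and rolling entry would make memberships overlap, so that an 8-week cycle is not a real treatment group. At ICC 0.01 and 5 men per group almost nothing changes. The choice of variance formula and reference arm alone moves unclustered methamphetamine power from 80.9% to 84.0%, which is more than half of the loss at the middle assumption. Matching and covariate adjustment could also change the standard error, and the check above ignores both.

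Four stronger readings are tempting, and the documents do not support them.

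- A reader might infer that the plan will analyse the 600 men as independent. It plans mixed models and leaves the random effects undefined, so a group term is unspecified, not excluded.
- A reader might infer a known inflation of false non-inferiority claims. The 80% and the error rates above belong to a two-sided test of difference. Without a margin, non-inferiority power and error cannot be calculated.
- A reader might infer that dependence exists only on the group side. App participants may be recruited by paid referral (section 6.1.4), with up to three enrolled referrals per participant (section 6.5), so referral chains could create some on the app side too.
- A reader might take the claim of conservatism in section 8.3 as false. It concerns the use of two time points and says nothing about clustering.

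The core is untouched: the comparator was group-delivered, the stated effects match independence, and any positive ICC widens the correct interval.

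**Conclusion.** The concern holds as an unspecified model term and an unallowed-for design effect in Aim 1c. The direction is firm given any positive within-group correlation; the size is conditional. At an assumed ICC of 0.05, power falls to about 77-79% with 5 men per group, 74-76% with about 11, and 69-71% with 20. An analysis without a group term would run its nominal 5% test at about 5.8%, 6.9% and 8.8% respectively. At ICC 0.01 the power loss is about 0.5 to 2.5 points and hardly matters. No single figure, 74-76% included, should be quoted as the power of Aim 1c, because the documents do not give the inputs needed to choose one. This is worth correcting because Aim 1c carries the non-inferiority claim and the error favours the app.

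**What to change.** In the Aim 1c analysis section:

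- Describe how the historical groups were run (size, closed or rolling entry, number in parallel) and name the random effects.
- Fit a partially nested model with a random effect for treatment group in the brick-and-mortar sample. If group was not recorded or entry was rolling, use cluster-robust standard errors by intake period where dates exist.
- Base the app-versus-group conclusion on the resulting interval.
- Examine app-side dependence from referral chains as a sensitivity analysis.

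In Table 2 and the Aim 1c section, restate the detectable effects over a stated range of ICC and group size, for example about OR 1.57 / 0.605 / 0.646 at ICC 0.05 with about 11 men per group. In section 8.3, say that the claim of conservatism refers to the two-time-point basis and does not cover group clustering.

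The cost is SAP wording, one extra model term, slightly wider intervals and slightly less favourable detectable effects; no further participants are needed. The practical risk is data. Selecting men who attended after 2012 needs some attendance timing, but the documents do not show that group identifiers or exact dates were kept. The sponsor should check this before settling the model.

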10.0 DATA COLLECTION AND CONFIDENTIALITY

Data are collected for the purposes of this study; no other use will be made of the data. All assessment data will be collected via an ACASI administered by the Qualtrics system. All materials will be stored in Qualtrics' commercial cloud-based databases that are HIPAA compliant (secure and encrypted), which means all personal identifiers and any information that can be combined by any reasonable person to identify unique individuals will be stripped from the research record. Research materials are directly obtained from participants. Identification necessary to follow these individuals will be collected in order to maintain high follow-up rates necessary to answer the scientific aspects of the study.

The study consent form will inform participants of confidentiality guidelines. Strict confidentiality will be maintained; records that have personal identifiers (i.e., follow-up locator information) will be stored in a separate encrypted file from the assessment. Only the research team assigned to the follow-up of the participants will have access to non-anonymous records, and only for the purpose of contacting participants with reminders of their follow-up assessment. All research data are maintained in databases. No presentation or publication of the study results will refer to participants individually. Manuscripts published regarding this work will be based on the accumulated database. Additionally, the federal Certificate of Confidentiality, issued to all NIH-funded grants, protects subjects' records against subpoena. Exceptions to confidentiality for participants is any information that would lead to suspicion of child abuse, suspected abuse or neglect of elderly individuals, or dependent or vulnerable adults, or threat of imminent action on suicidal or homicidal ideation, which must be reported to the appropriate authorities. Participants will be informed of these exceptions during the informed consent process. In addition, representatives from the IRB will have limited access to the research record (e.g., to monitor the integrity of the research record).

10.1 Monitoring and Adverse Event Reporting

Adverse event reporting will follow the FRI policy. Serious adverse events (SAEs) include any of the following outcomes for the participant: 1) death; 2) acute life-threatening incidents; 3) hospitalization or the prolongation of a hospitalization; or 4) persistent or significant disability. SAEs may be communicated to the Principal Investigator by participants or staff, or may be observed directly by the Principal Investigator. SAEs will be reported regardless of whether they are considered project-related.

10.1.1 Regulatory Updates. The Principal Investigator will report any information related to unanticipated risks or new information that may change the risk-benefit ratio to the Western IRB. This information may come from the current project or findings from other projects or studies. Any changes in the protocol or consent as a result of this information will be promptly reported to the Western IRB. The Principal Investigator will also report any irregularities in the conduct of the project such as participant enrollment, obtaining informed consent, and data collection and processing.

10.1.2 Criteria for Premature Project Discontinuation. A participant may request to be self-withdrawn from study participation. A participant may be withdrawn from study participation by the Principal Investigator should a psychological condition make the risk to benefit balance of study participation unfavorable for the participant. The project may be discontinued at any time by NIH, or other government agencies as part of their duties to ensure that participants are protected.

